9.1.10 Photography

The investigator or trained study staff will photograph the subject's treatment area on Day 1, Day 8, Day 29, Day 84, and at early termination (if applicable). Prior to photographing the treatment area, study staff will (1) photograph a subject identification card including: subject's initials, subject number, visit day and date; and (2) place a light-balanced sticker in the treatment area.

9.1.11 Adverse Events

Information regarding occurrence of adverse events will be captured throughout the study. Duration (start and stop dates and times), severity/grade, outcome, treatment and relation to study drug will be recorded on the case report form (CRF).

9.2 Clinical Laboratory Measurements

9.2.1 Pregnancy Test

A urine pregnancy test will be obtained from female subjects who are of childbearing age prior to their participation in the study.

10 EVALUATIONS BY VISIT

All study visits will have a window +/- 3 days.

10.1 Visit 1 (Screening, Day -29 to 1)

1. Review the study with the subject (or subject's legal representative) and obtain written informed consent and HIPAA authorization.
2. Assign the subject a unique screening number.

3. Record demographics data.
4. Record medical history, including a history of actinic keratosis, diagnosis date, and prior AK treatments.
5. Record concomitant medications.
6. Perform a complete physical examination.
7. Perform and record vital signs.
8. Perform urine pregnancy test in female subjects of childbearing age.
9. Obtain informed consent.
10. Photography of treatment area.
11. Schedule subject for visit 2 in 0-29 days.

10.2 Visit 2 (Day 1, may be combined with Screening)

Unblinded investigator:

1. Randomization to treatment arms (1:1:1). Investigator will use sequential envelopes with randomly prefilled treatment arms. Envelopes will be filled in batches of three (nine patients) to ensure even allocation between arms during the course of treatment.
2. Perform and record vital signs.
3. Concomitant medications and Adverse Events review.

Blinded investigator:

4. Perform abbreviated physical examination.
5. Perform an AK count
6. Perform a pre-treatment local skin response assessment
7. Curette any hypertrophic AK
8. Application of ALA

Unblinded investigator:

9. Monitor ALA incubation duration depending on treatment arm
10. Light exposure (BLU-U and/or sunlight, depending on treatment arm)
11. Symptom assessment. All subjects will have symptom assessments at 15, 30, 45, 60, and 75 minutes (Table 2).
12. Skindex-16
13. Record any Adverse Events.
14. Photography of treatment area.

Blinded investigator:

15. Perform a post-treatment local skin response assessment

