8 STUDY TREATMENTS

8.1 Method of Assigning Subjects to Treatment Groups

Thirty eligible patients will be randomly assigned to one of three treatment arms (Conventional Arm, Combination Arm, Daylight Arm) in a 1:1:1 ratio using a SAS-based computer-generated randomization scheme developed by the study data management provider. The investigator or designee will complete a randomization worksheet prior to Visit 1.

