8.2 Blinding

This is a single-blinded study, as the subject cannot be blinded to treatment. AK counts, local skin reaction, and ALA application will be performed by the blinded investigator. History, concomitant medications, randomization, light exposure, symptom assessment, and Skindex-16 will be administered by the unblinded study coordinator.

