15.4 Analysis of Secondary Endpoints

Efficacy and tolerability data will be summarized by each secondary endpoint.

Symptom level over time during the treatment period will be graphed for visualization along the three axes of pain, stinging/burning, and itching/pruritus as well as a composite symptom score. Peak symptom level during the treatment period and pain at the end of treatment exposure will be compared between the conventional treatment arm (A), the combination treatment arm B), and the daylight treatment arm (C), with unpaired t-tests.

Percent reduction in the number of actinic keratoses and proportions of patients with partial and complete clearance of actinic keratoses will be presented descriptively and visualized as histograms. We will compare the percent reduction in the number of AKs and the proportions of patients with clearance between the conventional treatment arm (A) and the combination treatment arm B), and between the conventional treatment arm (A) and the daylight treatment arm (C), using unpaired t-tests.

All analyses will be based on the intent-to-treat (ITT) population. In the ITT population, patients will be counted in the treatment group upon randomization, regardless of receiving any dose of study medication. For efficacy analysis, all missing values due to patient early termination from the study will be imputed using last observation carried forward (LOCF) method, as appropriate. For each patient, the Baseline values will be defined as those values recorded at Day 1 prior to dosing. Patients who are lost-to-follow-up after Baseline will be included to the ITT population carrying forward their Baseline values.

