APPENDIX III. TIMING OF SYMPTOM ASSESSMENTS

Min	Symptom Assessment	Conventional Arm	Combination Arm	Daylight Arm
0		Begin 1 hour Incubation	Begin 15 minute incubation	Begin 15 minute incubation
5		Incubation	Incubation	Incubation
10		Incubation	Incubation	Incubation
15	X	Incubation	Sunscreen, BLU-U Exposure: 16m 40s	Sunscreen, Daylight Exposure: 60m
20		Incubation	BLU-U	Daylight
25		Incubation	BLU-U	Daylight
30	X	Incubation	End BLU-U, Begin Daylight Exposure: 60m	Daylight
35		Incubation	Daylight	Daylight
40		Incubation	Daylight	Daylight
45	X	Incubation	Daylight	Daylight
50		Incubation	Daylight	Daylight
55		Incubation	Daylight	Daylight
60	X	BLU-U Exposure: 16m 40s	Daylight	Daylight
65		BLU-U	Daylight	Daylight
70		BLU-U	Daylight	Daylight
75	X	End BLU-U, Sunscreen	End Daylight	End Daylight

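### Randomization is the first step of Visit 2, although no listed procedure differs by arm until 15 minutes after ALA; opening the envelope later would protect the baseline and entry steps, but not the symptom endpoint

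*Combined protocol and SAP*

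**What the plan says.** Section 10.2 lists the Day 1 work as fifteen items grouped by role. Item 1, on the unblinded side, reads: "Randomization to treatment arms (1:1:1). Investigator will use sequential envelopes with randomly prefilled treatment arms". Items 4 to 8 belong to the blinded investigator: an abbreviated examination, the AK count, the pre-treatment skin assessment, "Curette any hypertrophic AK", and the ALA application. The first item that depends on the arm is item 9.

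Section 8.2 divides the roles in much the same way: "AK counts, local skin reaction, and ALA application will be performed by the blinded investigator", while "History, concomitant medications, randomization, light exposure, symptom assessment, and Skindex-16 will be administered by the unblinded study coordinator". On the subject it says: "This is a single-blinded study, as the subject cannot be blinded to treatment".

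In Appendix III the combination and daylight arms "Begin 15 minute incubation" at minute 0, when the conventional arm starts its one-hour incubation. The arms first differ at minute 15.

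Four other places bear on the point:

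- Section 8.1: "The investigator or designee will complete a randomization worksheet prior to Visit 1".
- Section 15.4 counts subjects by randomized arm "regardless of receiving any dose of study medication" and takes the Day 1 pre-dosing value as baseline.
- Section 12.3 rules out replacing subjects who withdraw.
- Section 14 describes the study as open-label, with the investigator able to see all data.

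**The concern.** An allocation should be revealed no earlier than it is needed. Here it is revealed before the baseline for a secondary endpoint is recorded, before curettage that could itself affect clearance, and before the subject is committed to treatment.

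Two kinds of harm are possible. The first needs a leak: the coordinator knows the arm, the subject may know it too, and nothing tells either to keep it from the assessor during items 4 to 8. The Day 1 AK count is the denominator of percent reduction, so a count influenced by the arm would carry into that endpoint.

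The second needs no leak. A subject can be drawn and then prove ineligible, be postponed or withdraw. Sections 1.1 and 2 say that the effective light dose varies with weather, and Section 10 allows visits to move by 3 days either way. Knowing the arm before dosing therefore leaves room for decisions that differ by arm. The documents do not say that this would happen; they leave it possible.

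**Working it through.** **1. When is the arm first needed?** Items 2 to 8 of Section 10.2 are the same for every arm. Appendix III has all arms in incubation from minute 0 until minute 15, when the combination arm starts BLU-U and the daylight arm starts daylight. The latest opening compatible with the schedule is just before minute 15.

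**2. Can the lesion rule first be checked after the draw?** Section 6.2 requires 4 to 20 lesions. Section 9.1.6 and Appendix I place an AK count at Screening, but the Visit 1 list in Section 10.1 has none. Screening and Day 1 may be combined. If Section 10 is followed as listed, the first count is item 5 of Visit 2, after the draw.

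**3. What does an undosed subject contribute?** Sections 9.1.8 and 10.2 and Appendix III list Day 1 symptom scores at 15, 30, 45, 60 and 75 minutes, and none earlier. The rule in Section 15.4 that carries baseline forward therefore has no symptom value to carry. With 10 per arm, each such subject is 1/10 = 10% of an arm.

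**4. Effect on power.** Section 15.6 states power 0.80 for a 1.25-point difference, 10 per arm, two-sided alpha 0.05. It gives no SD, so the figure can only be inverted. The t-test noncentrality is 1.25 / (SD × √(2/n)) with 2n − 2 degrees of freedom. Power 0.80 at n = 10 requires SD 0.943 (0.998 by the normal approximation). At SD 0.94:

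- n = 10: 1.25 / (0.94 × 0.4472) = 2.97; power 0.80.
- n = 9: 1.25 / (0.94 × 0.4714) = 2.82; power 0.75.

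The SD is an assumption. At SD 1.5 the pair is 0.42 and 0.38; at SD 2.0, 0.26 and 0.24; at SD 3.0, 0.14 and 0.13.

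**5. Effect of one lesion miscounted at baseline, if the blind leaks.** With B lesions at baseline and r left, percent reduction is 100 × (1 − r/B). Recording B + 1 raises it by 100r/[B(B + 1)]; recording B − 1 lowers it by 100r/[B(B − 1)]. The residual counts are illustrative.

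| B | r | True | B + 1 recorded | B − 1 recorded |
|---|---|---|---|---|
| 4 | 1 | 75.0% | 80.0% (+5.0) | 66.7% (−8.3) |
| 10 | 3 | 70.0% | 72.7% (+2.7) | 66.7% (−3.3) |
| 20 | 6 | 70.0% | 71.4% (+1.4) | 68.4% (−1.6) |

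At the limits of the lesion rule, a miscount can also change eligibility: 4 recorded as 3, or 20 recorded as 21, falls outside it.

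**6. What later opening leaves unchanged.** The planned sample size, alpha and nominal power stay the same. So does block predictability. If each batch of nine envelopes is a permuted block with three per arm, on average 1.29 of 9 assignments (14.3%) are certain beforehand, and a best guess is right 53.2% of the time against 33.3% by chance.

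**The case against.** The strongest reply is that the blind already covers the steps in question. Sections 8.2 and 10.2 give the count, the skin assessment and the ALA application to a blinded investigator, and Section 10.2 adds curettage. On paper, the person doing this work does not know the arm. That stands: the measurement route depends on a leak, and a miscount that does not differ by arm is only noise. The reply is weakened by Section 14, which calls the study open-label, and by the lack of any instruction to withhold the arm from the subject until item 8.

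On eligibility, Section 4.1 has screening data reviewed before entry and Section 8.1 speaks of randomizing eligible patients. The intention is clear, but the visit list that staff would follow does not carry it out.

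The lists may also not be a strict timeline. Symptom assessment is item 11, after light exposure at item 10, although it runs during the exposure; Section 10.1 lists consent twice. Even so, item 1 is most naturally read as first.

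Finally, a later draw does not stop a subject from declining the assigned light. Part of the problem moves from not dosed to dosed but not treated as assigned. That also stands.

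**Conclusion.** The point holds as a cheap design improvement of modest weight. The order of steps and the common path to minute 15 are plain in the documents. Later opening would protect the baseline count, the pre-treatment skin assessment, curettage, ALA application and the entry decision. The entry route is the firmer argument, because it needs no breach of the blind. Its size is 10% of an arm per undosed subject; how many there would be cannot be known from the documents.

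Three stronger readings are tempting and are not supported:

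- A reader might infer that later opening removes bias from the trial. The primary endpoint is reported by an unblinded subject to an unblinded coordinator, and the change does not touch that. Nor does it prevent unblinding at later AK counts and skin assessments, or prediction within a block.
- A reader might infer that it costs nothing. That is true of planned sample size, alpha and nominal power, but the documents do not let one judge the logistics.
- A reader might take one miscounted lesion to be worth 1/4 = 25 points at 4 lesions and 1/20 = 5 points at 20. For a baseline error, shifts near those sizes arise only if almost nothing clears. With most lesions cleared they are 5 to 8 points and about 1.5 points.

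**What to change.** - Move the draw in Section 10.2. The unblinded coordinator opens the next envelope only after eligibility (including the lesion count), the baseline AK count, the pre-treatment skin assessment and curettage are recorded. Preferably this is after ALA application, before minute 15. If that leaves too little time, opening after curettage and before ALA still protects the count, curettage and the eligibility check.
- Reconcile Section 8.1. If the worksheet completed before Visit 1 carries the assignment, a later envelope achieves nothing. State what the worksheet contains and who sees it.
- Reconcile the Visit 1 list in Section 10.1 with Section 9.1.6 and Appendix I on the screening AK count. For combined visits, state that the lesion rule is confirmed before the draw.
- Reconcile the open-label statement in Section 14 with Section 8.2, and instruct staff and subjects not to disclose the arm to the blinded investigator.
- Report by arm the number randomized but not dosed, and the number dosed but not given the assigned light.

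The cost is re-ordering one list and aligning three or four sentences. The downside is that staff must be ready for any arm at short notice, and a subject may still decline the assigned light once it is known.

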6.3 Exclusion Criteria

- Subjects with any dermatologic disease in the treatment area that may be exacerbated by the treatment proposed or that might impair the evaluation of AKs.
- Subjects who are currently participating in another clinical study or have completed another clinical study with an investigational drug or device on the study area within 30 days prior to study treatment initiation.

- Subjects with any medical condition that in the opinion of the investigator, makes the patient unsuitable for the trial.

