14 DATA SAFETY MONITORING

Due to the scope of this study, there will be no formal Data Safety Monitoring Board (DSMB) or Data Monitoring Committee (DMC). This is an open-label, single-center study for an FDA-approved medication, and the investigator will have access to all study data.

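### Section 10.2 tells the unblinded staff who open the envelopes the fixed batch size, so about 4 of 30 allocations can be known in advance

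*Combined protocol and SAP*

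**What the plan says.** All references are to the combined protocol and SAP.

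- **Mechanism (10.2).** Randomization is the first step of Visit 2, listed under the unblinded investigator: "Investigator will use sequential envelopes with randomly prefilled treatment arms". The next sentence gives the batch size: "Envelopes will be filled in batches of three (nine patients) to ensure even allocation between arms during the course of treatment".
- **Who knows past allocations (8.2, 14).** Section 8.2 says that "randomization, light exposure, symptom assessment, and Skindex-16 will be administered by the unblinded study coordinator". Section 14 adds: "This is an open-label, single-center study for an FDA-approved medication, and the investigator will have access to all study data". One site means one envelope sequence to follow.
- **Room for discretion at entry.** Section 10.1 ends with "Schedule subject for visit 2 in 0-29 days", and section 10 adds "All study visits will have a window +/- 3 days". Day 1 may also be combined with screening. Section 6.3 excludes a subject with a medical condition that, "in the opinion of the investigator, makes the patient unsuitable for the trial".
- **Source of the list (8.1).** The data management provider develops a computer-generated scheme; no block size is given there. The same section has a randomization worksheet completed before Visit 1, which does not fit randomization at Visit 2.

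The text does not mention sealed or opaque envelopes, varying block sizes, or keeping the block size from site staff.

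**The concern.** Concealment requires that whoever enters a subject cannot foresee the next arm. Here the same unblinded staff have the two facts needed to forecast it: the allocations already used and the size of the batch. As a batch runs down, arms drop out of contention, and the last envelope is always known.

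A foreseeable arm could influence whether a borderline subject is entered, or when. Blinded AK counts and skin scoring (8.2) protect assessment, but they do not protect the make-up of the arms. The primary comparison is an unadjusted unpaired t-test (15.3) on symptoms reported by subjects who know their treatment.

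With 10 subjects per arm, small shifts in composition can show. As an illustration on an assumed scale: if two subjects in different arms would differ by *d* points in pain, exchanging them moves each mean by *d*/10 and the difference by 2*d*/10. For *d* of 2 to 5 points that is 0.4 to 1.0 point, beside the 1.25-point difference that section 15.6 says the trial can detect.

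**Working it through.** The plan gives no figure for predictability, so there is none to reproduce.

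**Inputs.** Batch of nine (10.2); three arms, 1:1:1, 30 subjects at one site (synopsis, 4.1). Assumption: exactly three envelopes per arm in each batch.

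**Method.** Staff always guess the arm with most envelopes left. If the remaining counts are (a, b, c), the chance of a correct guess is max(a, b, c)/(a + b + c). This is averaged exactly over all orderings of a batch.

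| Position in batch | 1 | 2 | 3 | 4 | 5 | 6 | 7 | 8 | 9 |
|---|---|---|---|---|---|---|---|---|---|
| Best guess correct | 0.333 | 0.375 | 0.429 | 0.446 | 0.471 | 0.536 | 0.571 | 0.625 | 1.000 |
| Arm certain | 0 | 0 | 0 | 0 | 0 | 0 | 0.036 | 0.250 | 1.000 |
| At least one arm ruled out | 0 | 0 | 0 | 0.036 | 0.143 | 0.357 | 0.679 | 1.000 | 1.000 |

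The certainty row can be checked by hand:
- Position 9: one envelope left, always known.
- Position 8: the last two are the same arm with probability 9/36 = 0.250.
- Position 7: the last three are the same arm with probability 3/84 = 0.036.

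**Per full batch.** Correct guesses 4.787 of 9 (53%), against 3 of 9 by chance. Certain 0.036 + 0.250 + 1 = 1.286 of 9 (14%). At least one arm ruled out 3.214 of 9.

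**Over 30 subjects** (three full batches, then the first three envelopes of a fourth):
- Correct: 3 × 4.787 + (0.333 + 0.375 + 0.429) = 15.5, or 51.7%, against 10 by chance.
- Certain: 3 × 1.286 + 0 = 3.9, or 12.9%.
- At least one arm ruled out: 3 × 3.214 + 0 = 9.6.

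**Does varying the block size help?** Expected correct guesses of 30, from 60,000 simulated sequences, guessing the least-used arm so far:

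| Scheme | Correct of 30 |
|---|---|
| Fixed 9 | 15.5 |
| Random 6/9/12 | 15.5 |
| Random 3/6/9 | 16.4 |
| Random 3/6 | 17.2 |
| Simple randomization | 10.0 |

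Varying the size does not lower the average rate, and small blocks raise it. What it removes is certainty, provided the sizes stay hidden.

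**Balance under the present scheme.** 30 = 3 × 9 + 3. If the fourth batch is also a block of nine, its first three envelopes contain one of each arm with probability 27/84 = 0.32. So 10/10/10 is not assured now.

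**The case against.** The strongest reply is that this is a small descriptive study with an ordinary envelope scheme, and that steering is conjecture. Much of that stands.

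- **A reader might infer that subjects will be steered**, for instance by booking a foreseeable daylight subject for a bright day. The documents do not support that. They do not say who schedules Visit 2. The date is set at Visit 1, up to 29 days ahead, and there is nothing to schedule when the visits are combined. With 30 subjects over about 12 months (synopsis), accrual is about 2.5 a month, so at an even pace few subjects would be waiting together.
- **A reader might take the section 6.3 exclusion as open discretion.** It requires a medical condition, and no listed screening procedure measures pain sensitivity.
- **A reader might infer that nothing later could reveal or correct selection because symptoms are self-reported by unblinded subjects.** That does not follow. Unblinded self-report is a measurement problem, separate from selection at entry. Demographics, medical history and Day 1 AK counts are collected, so some imbalance would be visible.
- **A reader might take batches of three to mean blocks of three.** The rates would then be (1/3 + 1/2 + 1)/3 = 61% correct and 10 of 30 certain. The parenthesis giving nine patients points to nine, and the text does not confirm the other reading.
- **Part of the remedy already exists:** a provider-generated scheme (8.1) and sequential envelopes (10.2). Silence on sealing does not show that the envelopes will be unsealed.

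The reply does not touch the core: the batch size is disclosed to the people who open the envelopes and know what has gone before, and the plan gains nothing from that disclosure.

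**Conclusion.** The point holds as a concealment weakness that is cheap to repair. With batches of nine and three per arm, the best guess is right for about 15.5 of 30 subjects (52%, against 33%), and about 4 of 30 allocations are certain beforehand.

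The figures assume exactly three per arm in every batch, staff who keep track of past allocations, and a fourth batch built like the others. They measure opportunity. They are neither evidence of selection nor an estimate of bias in the pain comparison, and the documents offer no basis for one.

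Nor should a reader infer that varying blocks would bring guessing down towards chance: the average rate stays at 15.5 of 30 or rises.

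**What to change.** 1. Delete the batch size from section 10.2.
2. Have the data management provider named in 8.1 generate the list with varying block sizes that avoid very small blocks (for example 6/9/12), and hold the sizes off site in a restricted document until database lock.
3. Have the same provider prepare sequentially numbered, sealed, opaque envelopes.
4. State that each envelope is opened only after eligibility and the Visit 2 date have been recorded.
5. Reconcile the worksheet completed before Visit 1 (8.1) with randomization at Visit 2 (10.2).

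The cost is a few sentences and a new list, or a new list for the envelopes not yet used if enrolment has begun. Arm sizes may end slightly unequal, which the present scheme does not rule out either.
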